6.3. Follow-up Assessments

6.3.1. 2-Week Follow-up (In-Person, Phone Call or Telehealth Visit)

A 2-week follow-up visit, which may occur in person, by telephone or as a telehealth visit, will occur 10-14 days after permanent implant. The 2-week follow-up visit provides an opportunity for the site to confirm that the patient understands the charging plan and has the opportunity to report any adverse events. If the clinician programmer is connected to the subject's IPG all reports will be downloaded. The following data will be collected:

- All serious adverse events including deaths (if applicable)
- Non-serious adverse events related to device/procedure/stimulation/charging/MRI (if applicable)
- Charging history (if applicable)
- Stimulation programs used since permanent implant (if applicable)
- Stimulation programs available at the end of the visit (if applicable)
- Withdrawal (if applicable)
- Device Deficiency (if applicable)
- Additional Surgery (if applicable)

6.3.2. 6-Week Follow-up (In-Person Visit)

Subjects will be followed at a 6-week follow-up visit that will occur 30-45 days after permanent implant. The following data will be collected:

- All serious adverse events including deaths (if applicable)
- Non-serious adverse events related to device, procedure, stimulation, charging, or MRI (if applicable)

Clinical Investigation Plan

- NRS
- PROMIS-29
- Patient satisfaction
- Patient charging experience
- Charging history
- Stimulation programs used since permanent implant
- Stimulation programs available at the end of the visit
- Withdrawal (if applicable)
- Device Deficiency (if applicable)
- Additional Surgery (if applicable)

During the 6-week follow-up visit, site personnel will connect to the subject's IPG using the CP. Site personnel will use the CP to collect the charging history, programming and program use details as PDF files.

6.3.3. Patient Reported Outcome (PRO) Measures

The Coordinator or designee will administer the patient-reported outcome questionnaires, via paper for later transcription to EDC. It is important the subject understands the meaning of all words and instructions in the questionnaires. The subject should be instructed to ask any questions about the questionnaires if further explanation is needed. Once the questionnaires are completed, the Coordinator or designee will review for completeness to verify that all questions have been answered according to the directions provided.

The following validated PRO measures will be collected:

- NRS for pain intensity
- PROMIS-29

6.3.3.1. Pain Numerical Rating Score (NRS)

The pain NRS consists of 1 question that will be asked by interviewing the subjects. Patients will be asked to rate, from 0 (no pain) to 10 (worst imaginable pain), their pain at the time of study visit specific to the area(s) of chronic pain being treated. A higher score indicates greater pain intensity.

6.3.3.2. Patient-Reported Outcome Measure Information System (PROMIS-29)

The PROMIS-29 is an adult scale developed in partnership with the National Institutes of Health (NIH) in the United States to estimate overall quality of life by assessing the following domains known to impact activities of daily living: physical function, sleep disturbance, depression, anxiety, fatigue, pain interference, pain intensity, and social role satisfaction. The scale requires subjects to rate the frequency and/or severity of symptoms and experiences related to each of these domains. A total score is calculated and transformed against normative data into a t score indicating global quality of life in relation to population norms. Subscales are defined by each domain described above and can be examined separately to parse separate symptoms or deficiencies in quality of life. The final item is an 11-point pain intensity numerical rating scale (NRS) by which the subject rates their average pain over the past 7 days. Subjects should read each item and check the one box that most closely represents their response.

Clinical Investigation Plan

6.3.4. Unscheduled Visits

An unscheduled visit is defined as a visit that occurs between the required follow-up visits for non-standard of care issues, such as a potential or actual adverse event. If the clinician programmer is connected to the subject's IPG all reports will be downloaded. Any data collected related to the clinical study endpoint should be documented by completing the appropriate CRF (see schedule of events table).

Following an unscheduled visit, the subject will be seen for the next scheduled study visit within window.

6.3.5. Schedule of Events

Clinical Investigation Plan

CIP Activity	Enrollment	Baseline	Permanent Implant Procedure	Follow-up visits 2-week (10-14 days post implant)	Follow-up visits 6-week (30-45 days post implant)	Unscheduled visit
Subject evaluated for eligibility	X					
Informed Consent Process	X					
Demographics		X				
Medical History		X				
Pain diagnosis and pain location		X				
NRS for pain intensity		X			X	
PROMIS-29		X			X	
Patient charging experience					X	
Patient Satisfaction					X	
Implant procedure and system data			X			
Device Programming			X	(X)	X	(X)
Charging History				(X)	X	(X)
Stimulation programs used				(X)	X	(X)
Stimulation programs available			X	(X)	X	(X)
Device deficiency			(X)	(X)	(X)	(X)
Additional surgery (System revision, Replacement/Explant)				(X)	(X)	(X)
Serious adverse events		(X)	(X)	(X)	(X)	(X)
Procedure- Device-charger- stimulation- MRI-related Adverse Events			(X)	(X)	(X)	(X)
Withdrawal		(X)	(X)	(X)	(X)	(X)

(X)-Indicates event may occur at visit

Clinical Investigation Plan

7. Adverse Events

To comply with worldwide standards and guidelines on clinical investigation adverse event reporting, the Sponsor has adopted uniform and worldwide applicable standard definitions and reporting timelines to be used and adhered to by the investigators.

7.1. Definition

7.1.1. Adverse Event

An adverse event (AE) is any untoward medical occurrence, unintended disease or injury, or untoward clinical signs (including abnormal laboratory findings) in subjects, users or other persons, whether or not related to the medical device under investigation.

As part of ISO14155 Section 3.2, the Adverse Event definition has the following notes:

Note 1: This definition includes events related to the medical device under investigation or the comparator.

Note 2: This definition includes events related to the procedures involved.

Note 3: For users or other persons, this definition is restricted to events related to medical devices under investigation.

7.1.2. Serious Adverse Event

If the AE meets any of the criteria below, it is regarded as a serious adverse event (SAE).

- a) Led to a death,
- b) Led to a serious deterioration in health of the subject, that either resulted in
 1. a life-threatening illness or injury, or
 2. a permanent impairment of a body structure or a body function, or
 3. in-patient hospitalization or prolongation of existing hospitalization, or
 4. medical or surgical intervention to prevent life threatening illness or injury or permanent impairment to a body structure or a body function.
 5. chronic disease
- c) Led to fetal distress, fetal death or a congenital abnormality or birth defect.

Note: A planned hospitalization for a pre-existing condition, or a procedure required by the CIP without a serious deterioration in health, is not considered to be an SAE.

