7.2.1. Unanticipated (Serious) Adverse Device Effect [U(S)ADE]

Unanticipated serious adverse device effect (USADE) refers to any serious adverse effect on health or safety or any life-threatening problem or death caused by, or associated with, a device, if that effect, problem or death was not previously identified in nature, severity, or degree of incidence in the investigational plan or application (including a supplementary plan or application), or any other unanticipated serious problem associated with a device that relates to the rights, safety, or welfare of subjects.

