7.3. Adverse Event and Device Deficiency/Device Malfunction Reporting

7.3.1. Adverse Event Reporting

Safety surveillance and reporting starts as soon as the patient completes the ICF. All serious adverse events and any device-related adverse events, including those observed during the implant procedures and all-in-one/ on-table trials, will be reported.

Safety surveillance and reporting will continue until the subject performs the last follow-up visit, the subject is deceased, the subject concludes participation in the clinical investigation, or the subject withdraws from the clinical investigation. All serious and non-serious procedure- and device-related adverse event data, including deaths and device deficiency data, will be collected throughout the life of the study and will be reported to the Sponsor on a CRF. Additional information with regards to a procedure- and device-related adverse event should be updated within the appropriate CRF.

Unchanged, chronic, non-worsening or pre-existing conditions are not AEs and should not be reported.

The Sponsor will provide an offline form to allow the investigator to report SAEs in the event the entry cannot be made in the EDC. This does not replace the EDC reporting system. Sites must still enter all information in the EDC system as soon as feasible.

SAE Reporting

The investigator must report all SAEs to the Sponsor as soon as possible but no later than outlined below.

Clinical Site	Reporting timelines
All Sites	Sites must report SAEs to the Sponsor no later than 3 calendar days from the day the site personnel became aware of the event or as per

Clinical Investigation Plan

	the investigative site’s local requirements, if the requirement is more stringent than those outlined.
--	--

Sites must record the date the site staff became aware that the event met the criteria of an SAE in the source document. The Investigator will further report the SAE to the local EC according to the institution’s EC reporting requirements.

The following adverse events will be collected in this study for investigational devices as well as the approved devices:

- All serious adverse events including deaths
- Non-serious adverse events related to device/procedure/stimulation/Charging/MRI
- USADE
- DD

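### CIP 7.1.2(b) limits the non-fatal illness and injury criteria to the subject, although 7.1.1 counts device-related events in users and other persons, so serious non-fatal harm to them is classed as non-serious

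*Protocol*

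**What the plan says.** CIP 7.1.1 defines an adverse event as one occurring "in subjects, users or other persons, whether or not related to the medical device under investigation". Note 3 then narrows this for people who are not subjects: "For users or other persons, this definition is restricted to events related to medical devices under investigation". The wireless charger and its accessories are listed as investigational in CIP 2.2.1, so a charger-related event in such a person is an AE.

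CIP 7.1.2 takes any AE and calls it serious if it meets one of three criteria. Criterion (a) is death, with no person named. Criterion (b) begins "Led to a serious deterioration in health of the subject, that either resulted in" and governs five sub-items: life-threatening illness or injury, permanent impairment, hospitalisation, intervention to prevent these, and chronic disease. Criterion (c) is "Led to fetal distress, fetal death or a congenital abnormality or birth defect", again with no person named.

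On reporting, CIP 7.3.1 asks for "All serious adverse events and any device-related adverse events". For SAEs it sets a limit: "Sites must report SAEs to the Sponsor no later than 3 calendar days from the day the site personnel became aware of the event". It states no limit for non-serious device-related AEs.

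**The concern.** The two adjacent definitions cover different people. 7.1.1 deliberately brings in users and other persons; 7.1.2(b) leaves them out of every non-fatal illness or injury criterion. *Subject* cannot be read loosely as anyone harmed, because 7.1.1 has just distinguished subjects from users and other persons. The result is also incoherent: a device-related death in a user is an SAE, but a life-threatening injury to the same user is not.

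This bears on the study's purpose. CIP 1.1.2 says the study concentrates on safety events attributable to the new charging system, and that system includes external parts (charger, AC adapter, cable, charging apparel) that someone other than the subject might handle. At stake are the seriousness grade of such an event, its place among the SAEs reported under CIP 4.2 and SAP 3.2, and in some cases how quickly it reaches the sponsor and the regulator.

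**Working it through.** No figure in the plan bears on this point and no arithmetic applies. The check is to take one event and follow it through the definitions.

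**Test event.** A non-fatal injury to a user or other person that is life-threatening or leads to hospitalisation, and is related to an investigational component.

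1. *Is it an AE?* Yes. 7.1.1 covers users and other persons, and Note 3 is met because the event is device-related.
2. *Is it an SAE?*
   - Criterion (a): no, because there is no death.
   - Criterion (b): no, because the deterioration is not in the subject's health. All five sub-items fall with it.
   - Criterion (c): no, unless the outcome is fetal or congenital.
   - No other section extends (b). The event is therefore a non-serious AE.
3. *Is it still reported?* Yes. 7.3.1 requires any device-related AE to be reported, and CIP 3.2 has the CEC adjudicate non-serious device-related AEs. Neither section gives a deadline for these, and neither says that CEC review can make such an event an SAE.
4. *Does another 3-day route apply?*

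| Route | Covers non-subjects? | Limit | When it fails |
|---|---|---|---|
| SAE (7.1.2, 7.3.1) | Only for death or a fetal or congenital outcome | 3 calendar days | Any other non-fatal illness or injury |
| Device deficiency (7.1.3, 7.3.3) | Yes; not tied to who is harmed, and includes misuse, use error and inadequate labelling | 3 calendar days | No deficiency identified |
| USADE (7.2.1, 7.3.2) | Yes; covers "any serious adverse effect on health or safety or any life-threatening problem or death caused by, or associated with, a device" | 3 calendar days | The effect was already identified in nature, severity and incidence |
| Non-serious device-related AE (7.3.1) | Yes | None stated | – |

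5. *What remains?* The 3-day limit is lost only when the last row alone applies: serious, non-fatal, device-related harm to a non-subject, from an anticipated effect, with no identified deficiency. Of the three charging effects listed as anticipated in CIP 15.2 (heating or discomfort at staples, heating or discomfort at the pocket, interference with another implanted device), only the third could plausibly occur in someone else. The text does not say whose implant is meant.
6. *Regulator.* CIP 7.3.4 has the sponsor report SAEs and reportable deficiencies, per local requirements. In the residual case of step 5, neither category applies.
7. *Endpoint.* CIP 8.2.1 and SAP 2.3.1 count subjects with a related SAE. A non-subject cannot enter that numerator or denominator, so the percentage and its Clopper-Pearson interval are the same under either wording of 7.1.2(b).

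**The case against.** The strongest reply is that the mismatch rarely matters, because other routes carry the same deadline. A charger that burns or shocks someone badly enough to need hospital care would very likely be reported as a device deficiency within 3 calendar days. Regulator reporting would probably follow too: 7.3.4 asks whether the deficiency might have led to an SAE in less fortunate circumstances, and since a subject uses the same charger, the same fault could have hurt the subject. An injury of that kind to another person is also not among the anticipated charging effects in CIP 15.2, so on the visible text it would be a USADE. The IB and IFU, which hold the fuller list, are not available here.

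All of this stands, and it limits the point. A reader might infer that serious charger harm to a caregiver can never be an SAE, goes unreported, or faces no deadline at all. The documents do not support that. A death would be an SAE under (a), the event is always a reportable device-related AE, and the deficiency and USADE routes would usually bring it in within 3 calendar days.

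The reply is also right about exposure. CIP 2.2.1 lists component names and models and mentions neither home use nor caregivers. Inclusion criterion 6 requires the subject to be able and willing to recharge, and CIP 6.2 has the subject instructed on the charger.

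What the reply does not answer is the classification. Neither alternative route makes the event an SAE, and neither covers an anticipated effect with no identified deficiency.

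**Conclusion.** The inconsistency is real, and 7.1.1 and 7.1.2(b) should be reconciled. Its size is minor.

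- **Always lost:** the SAE classification, and therefore the SAE listing, for serious non-fatal illness or injury in a user or other person. All five sub-items of (b) are affected.
- **Lost only in the residual case** (anticipated effect, no identified deficiency): the 3-day SAE report and SAE reporting to the regulator.
- **Not affected:** the confirmatory percentage and its interval.

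This is a gap in a safety definition, not a statistical error. It rests on the text of the CIP alone; the CIP cites ISO 14155:2020, but the standard's own SAE wording is not in the documents and is not relied on. That people other than the subject are exposed to the charger is an assumption. The documents give no expected number of such events; they would be rare.

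**What to change.** In CIP 7.1.2(b), replace *of the subject* with *of the subject, a user or another person (for users and other persons, device-related events only, as in 7.1.1 Note 3)*.

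In SAP 3.2, add a separate listing for any SAEs in users or other persons, kept outside the per-subject percentages so that those denominators still refer to study subjects.

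The cost is one phrase in the CIP and one listing in the SAP. The downside is an occasional extra SAE report. Design, sample size and the confirmatory analysis stay as they are.

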7.1.3. Device Deficiency/Device Malfunction (if applicable)

Device deficiency is defined as an inadequacy of a medical device related to its identity, quality, durability, reliability, safety or performance, such as malfunction, misuse or use error and inadequate labeling. This includes the failure of the device to meet its performance

Clinical Investigation Plan

specifications or otherwise perform as intended. Note: performance specifications include all claims made in the labeling of the device.

A device malfunction is the failure of a device to meet its performance specifications or otherwise perform as intended, when used in accordance with the instructions for use or CIP.

Clinical Investigation Plan

7.2. Device Relationship

Determination of whether there is a reasonable possibility that an investigational product or device under investigation caused or contributed to an AE is to be **determined by the Investigator** and recorded on the appropriate CRF form. Determination should be based on the assessment of temporal relationships, evidence of alternative etiology, medical/biologic plausibility and patient condition (pre-existing condition).

7.2.1. Unanticipated (Serious) Adverse Device Effect [U(S)ADE]

Unanticipated serious adverse device effect (USADE) refers to any serious adverse effect on health or safety or any life-threatening problem or death caused by, or associated with, a device, if that effect, problem or death was not previously identified in nature, severity, or degree of incidence in the investigational plan or application (including a supplementary plan or application), or any other unanticipated serious problem associated with a device that relates to the rights, safety, or welfare of subjects.

7.3. Adverse Event and Device Deficiency/Device Malfunction Reporting

7.3.1. Adverse Event Reporting

Safety surveillance and reporting starts as soon as the patient completes the ICF. All serious adverse events and any device-related adverse events, including those observed during the implant procedures and all-in-one/ on-table trials, will be reported.

Safety surveillance and reporting will continue until the subject performs the last follow-up visit, the subject is deceased, the subject concludes participation in the clinical investigation, or the subject withdraws from the clinical investigation. All serious and non-serious procedure- and device-related adverse event data, including deaths and device deficiency data, will be collected throughout the life of the study and will be reported to the Sponsor on a CRF. Additional information with regards to a procedure- and device-related adverse event should be updated within the appropriate CRF.

Unchanged, chronic, non-worsening or pre-existing conditions are not AEs and should not be reported.

The Sponsor will provide an offline form to allow the investigator to report SAEs in the event the entry cannot be made in the EDC. This does not replace the EDC reporting system. Sites must still enter all information in the EDC system as soon as feasible.

SAE Reporting

The investigator must report all SAEs to the Sponsor as soon as possible but no later than outlined below.

Clinical Site	Reporting timelines
All Sites	Sites must report SAEs to the Sponsor no later than 3 calendar days from the day the site personnel became aware of the event or as per

Clinical Investigation Plan

	the investigative site’s local requirements, if the requirement is more stringent than those outlined.
--	--

Sites must record the date the site staff became aware that the event met the criteria of an SAE in the source document. The Investigator will further report the SAE to the local EC according to the institution’s EC reporting requirements.

The following adverse events will be collected in this study for investigational devices as well as the approved devices:

- All serious adverse events including deaths
- Non-serious adverse events related to device/procedure/stimulation/Charging/MRI
- USADE
- DD

7.3.2. Unanticipated Serious Adverse Device Effect Reporting to Sponsor and IRB (if applicable)

The Sponsor requires the Investigator to report any USADE to the Sponsor within 3 calendar days of the investigator’s knowledge of the event, unless local requirements are more stringent, and to the EC per EC requirements.

7.3.3. Device Deficiency/Malfunction Reporting (if applicable)

Sites should report all device deficiencies/malfunctions on the appropriate CRF form.

The investigator must report all device deficiencies/malfunctions to the Sponsor as soon as possible but no later than outlined below.

Clinical Sites	Reporting timelines
All Sites	Sites must report device deficiencies/malfunctions to the Sponsor no later than 3 calendar days from the day the site personnel became aware of the event or as per the investigative site’s local requirements, if the requirement is more stringent than those outlined.

Sites must report device deficiencies/malfunctions to the EC per the investigative site’s local requirements.

In the event of a device deficiency/malfunction and the investigational device is not implanted, sites should return the device to the Sponsor.

If investigational devices are explanted for any reason, the investigator should arrange for the device to be returned to the Sponsor. See appendix VII for additional details.

All investigational device explant procedures shall be performed at the discretion of the study investigator, and should follow the specific processes of the participating site.

Clinical Investigation Plan

Sites will have access to an offline form to allow the investigator to report device deficiencies/malfunctions if sites cannot enter the information in the EDC system. This does not replace the EDC reporting system. Sites must still enter all information in the EDC system as soon as feasible.

Sites should report all device deficiencies/malfunctions to the Sponsor's Customer Service Department.

